5.1.6 Analysis visit window

In general, the analysis visit window will not be derived, and the visits will be used as reported on the electronic case report form (eCRF). If the derivation of analysis visit window is needed, the following analysis visit window approach will be applied:

- If the assessments are collected at a scheduled visit, the collected data will be mapped to the nominal scheduled visit;
- If the assessments are not collected at a scheduled visit but are collected at an unscheduled visit, the collected data will be mapped based on the analysis window derived as lower bound (exclusive) at the midpoint between the given scheduled visit and preceding scheduled visit, and upper bound (inclusive) at the midpoint between the given scheduled visit and next scheduled visit according to the scheduled visits for corresponding assessments as outlined in Table 1 and Table 2;
- If more than one assessments (not replicate/triplicate assessments) occur within a given analysis visit, the assessment closest to the target study day will be used. In case of ties between assessments located on different sides of the target day, the later assessment will be used. In case of ties located on the same side of the target day, the value with the later entry date/time will be used.

5.2 Participant characteristics

5.2.1 Participant disposition

Participant disposition will be summarized for the ITT population using the number and percentage of participants who are randomized, who are randomized but do not receive the study treatment, who are treated, who complete the study, and who early withdraw from the study and primary reason for early withdrawal from the study.

A separate summary will be provided for the number and/or percentage of participants who are screened, and who screen failures and reason for screen failures.

Participant disposition will be listed for all randomized participants. Participants who are screen failures as well as the eligibility status for the study will be listed for all screened participants as well.

5.2.2 Protocol deviations

Protocol deviations will be identified and categorized in the eCRF, and designated as major/critical or minor.

The major/critical protocol deviations will be summarized by category for the ITT population.

All protocol deviations will be presented in a listing.

5.2.3 Demographics and baseline characteristics

Demographics and other baseline characteristics will be summarized using the ITT population. The demographics characteristics will include age groups (school-age children (5 to 14 years-old) and young adults (15 to 18 years-old), gender, weight, height, body mass index (BMI). Other baseline characteristics will include photophobia, blurred vision, visual impairment, pruritus, skin lesions compatible with scabies, serum HIV test (Mozambique only), body temperature, blood pressure, heart rate, respiratory rate.

The baseline parasitological testing results, including number and percentage of participants who are positive for *Trichuris trichiura*, *Ascaris lumbricoides*, Hookworm, Haematuria, *Strongyloides stercoralis* will be presented.

Bivariate analysis of baseline demographics characteristics between screen failure participant and randomized participant may be presented.

Individual demographics and baseline characteristics will be listed.

5.2.4 Concomitant medications

Concomitant medications are defined as any medications that were ongoing or started on or after the first dose of study treatment.

Medications will be recorded and coded using the latest version of World Health Organization (WHO) Drug Enhanced Dictionary. Concomitant medications will be summarized by Anatomical Therapeutic Chemical (ATC) classification pharmacological or therapeutic subgroup (Level 2) and preferred drug name for the safety population. At each level of summarization, a participant is counted once if he/she reported 1 or more medications at that level.

The by-participant listing will be provided for prior and concomitant medications.

5.2.5 Concomitant diseases

The concomitant diseases will be coded using the latest version of Medical Dictionary for Regulatory Activities (MedDRA).

The concomitant diseases will be summarized by system organ class (SOC) and preferred term (PT) in the safety population.

The by-participant listing will be provided for concomitant diseases.

5.2.6 Study drug administration

For the single dose treatment arms, the number and percentage of participants who receive study drug will be summarized. For the repeat dose treatment arm, the number and percentage of participants who receive 1, 2, or 3 doses of study drug will be provided.

Study drug administration will be presented in a data listing.

5.3 Efficacy analysis

5.3.1 Hypothesis

The main hypothesis is that FDC (either at single or 3-day regimens) will be more effective against STH than the current strategy (single dose ALB alone).

Specific hypotheses:

- Primary Efficacy Endpoint: Higher estimated CR for *T. trichiura* 21 days after treatment, using microscopy in participants allocated to arms 2 and 3 than to arm 1.
- Secondary Efficacy Endpoint(s):
 - Higher estimated CR for hookworm and *S. stercoralis* 21 days after treatment using microscopy in participants allocated to arms 2 and 3 than to arm 1.
 - Higher estimated ERR for *T. trichiura* 21 days after treatment using microscopy in participants allocated to arms 2 and 3 than to arm 1.
 - Higher estimated CR for hookworm, *T. trichiura* and *S. stercoralis* 21 days after treatment, using qPCR in participants allocated to arms 2 and 3 than to arm 1.

5.4 **Primary efficacy outcomes analysis**

The primary efficacy endpoint for the efficacy phase III trial is the cure rates for *T. trichiura* 21 days after treatment using microscopy. The analysis will be conducted on the ITT population and in the sensitivity population (per protocol). The analysis will include both Phase II and Phase III participants. The Cochran–Mantel–Haenszel (CMH) test, controlling the effect of site if that is appropriate (sufficient participants), will be used to compare the cure rates for the 3 treatment groups. A participant is considered cured if the baseline egg count or larval count is not 0, and the post-treatment egg count or larval count is 0. Similarly, a participant is considered to have treatment failure if the baseline egg or larval count is not 0.

A total of 2 stool samples (1 pre-treatment and 1 post-treatment) will be obtained from each participant. The primary efficacy analysis will be based on ITT population. Efficacy for each type of infection will be analysed separately. A participant with multiple infections will be included in the analysis of each target species that the participant is infected with.

Stool sample collected pre-treatment will be used for the baseline information, and stool sample collected post-treatment will be used for the post-treatment information in the statistical analysis.

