#### 6.1.2 DOSING AND ADMINISTRATION

# Phase II component

Participants will be randomly allocated with equal probability to receive either:

Treatment Arm 1: Single dose of a tablet of ALB

Treatment Arm 2: Single dose of a tablet of FDC

Treatment Arm 3: Daily dose of a tablet of FDC for 3 days.

and will be recruited by  $\mu g/Kg$  of IVM to be received in a sequential manner starting from Group 1 through to Group 3 as shown below:

- Group 1: receiving 300-391  $\mu$ g/Kg or ALB 400mg- 38 participants (body weight: 23-<30 Kg) will be recruited in this group. (FDC 400mg-9mg).
- Group 2: receiving 400-600  $\mu$ g/Kg or ALB 400mg– 38 participants (body weight: 30-45 Kg) will be recruited in this group. (FDC 400mg-18mg).
- Group 3: receiving 391-600 μg/Kg or ALB 400mg- 50 participants (body weight: 15-23 Kg) will be recruited in this group. (FDC 400mg-9mg).

Group 2 will receive FDC in an Albendazole 400mg/Ivermectin 18mg comp, groups 1 and 3 will receive FDC in an Albendazole 400mg/Ivermectin 9mg comp.

Version 4.0 ALIVE Study 21st January 2022

The table below shows the equivalent dose adjusted per weight received from 15 to 45 kg:

		Equivalent dose			Equivalent dose
Weight (Kg)	Ivermectin Dose	received (μg/Kg)	Weight (Kg)	Ivermectin Dose	received (μg/Kg)
15	9	600	31	18	581
16	9	563	32	18	563
17	9	529	33	18	545
18	9	500	34	18	529
19	9	474	35	18	514
20	9	450	36	18	500
21	9	429	37	18	486
22	9	409	38	18	474
23	9	391	39	18	462
24	9	375	40	18	450
25	9	360	41	18	439
26	9	346	42	18	429
27	9	333	43	18	419
28	9	321	44	18	409
2 9	9	310	45	18	400
30	18	600			

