# Phase III Component

Participants will be randomly allocated with unequal probability, according to the specific expected cure rate by specie, to receive either:

**Treatment Arm 1**: Single dose of a tablet of ALB 400 mg (active control arm).

Treatment Arm 2: Single dose of a tablet of FDC 400mg-18mg or 400mg-9mg.

- o For participants <45 kg of body weight at baseline: FDC of 400mg ALB-9mg IVM.
- o For participants ≥45 kg of body weight at baseline: FDC of 400mg ALB-18mg IVM.

Treatment Arm 3: Daily dose of a tablet of FDC 400mg-18mg or 400mg-9mg for 3 days.

- o For participants <45 kg of body weight at baseline: FDC of 400mg ALB-9mg IVM.
- o For participants ≥45 kg of body weight at baseline: FDC of 400mg ALB-18mg IVM.

FDC will be provided as an oral dispersible formulation, while ALB will be a chewable pill. Both FDC and ALB will be taken with water after a light meal, followed by visual observation of the participant by the study physician at each site. Vomiting 1h post-treatment will require re-dosing. The participants will not

Version 4.0

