3. STUDY DESIGN

3.1 Design

Adaptive phase II/III trial to compare safety and efficacy of the active control arm (current standard of care) against 2 experimental arms.

Phase II component

Uni-centric, 3-arm, parallel, open-label, randomised, phase II trial to determine the safety and tolerability of FDC in paediatric population in different weight strata. Stratification by weight thus recruiting sequentially for safety and tolerability.

- Group 1 (38 participants): with body weight of [23-<30) Kg will receive 300-391 μ g/Kg (FDC 400mg-9mg) or ALB.
- Group 2 (38 participants): with body weight of [30-45] Kg will receive 400-600 μg/Kg (FDC 400mg-18mg) or ALB.
- Group 3 (50 participants): with body weight of [15-23) Kg will receive 391-600 $\mu g/Kg$ (FDC 400mg-9mg) or ALB.

ISGIODAI Barcelona Institute for Global Health

[figure not shown]

Figure 2. Phase II design (Kenya)

Phase III component

A Single-Blinded, Randomized, Multi-Centre, Parallel-Group, Active-Controlled, Superiority Study to Evaluate the Efficacy and Safety of a Single Day or 3-day Single Dose of FDC for the treatment of *Trichuris trichiura*, hookworm, *Strongyloides stercoralis* in paediatric and young adult population.

- a. Arm 1: Single dose of a tablet of ALB 400 mg (active control arm)
- b. Arm 2: Single dose of a tablet of FDC 400mg-18mg (≥45 kg of body weight at baseline) or 400mg-9mg (<45 kg of body weight at baseline).
- c. Arm 3: Daily dose of a tablet of FDC 400mg-18mg (≥45 kg of body weight at baseline) or 400mg-9mg for 3 days (<45 kg of body weight at baseline).

[figure not shown]

Figure 3. phase III design (Kenya, Ethiopia, Mozambique)

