3.3 Treatment

Phase II component

Participants will be randomly allocated with unequal probability to receive either:

Treatment Arm 1: Single dose of a tablet of ALB

Treatment Arm 2: Single dose of a tablet of FDC

Treatment Arm 3: Daily dose of a tablet of FDC for 3 days.

and will be recruited by μ g/Kg of IVM to be received in a sequential manner starting from Group 1 through to Group 3 as shown below:

- Group 1: receiving 300-391 μg/Kg or ALB 400mg- 38 participants (body weight: 23-<30 Kg) will be recruited in this group. (FDC 400mg-9mg).
- Group 2: receiving 400-600 µg/Kg or ALB 400mg− 38 participants (body weight: 30-45 Kg) will be recruited in this group. (Participants <45 kg: FDC of 400mg ALB-9mg IVM, participants ≥45 kg: FDC of 400mg ALB-18mg IVM).
- Group 3: receiving 391-600 μg/Kg or ALB 400mg- 50 participants (body weight: 15-23 Kg) will be recruited in this group. (FDC 400mg-9mg).

Phase III Component

Participants will be randomly allocated with unequal probability (Arm 1 p=0.2, Arm2 p=0.4, Arm3 p=0.4), according to the specific expected cure rate by specie, to receive either:

Treatment Arm 1: Single dose of a tablet of ALB 400 mg (active control arm).

- Treatment Arm 2: Single dose of a tablet of FDC 400mg-18mg or 400mg-9mg.
 - For participants <45 kg of body weight at baseline: FDC of 400mg ALB-9mg IVM.

◦ For participants ≥45 kg of body weight at baseline: FDC of 400mg ALB-18mg IVM.

Treatment Arm 3: Daily dose of a tablet of FDC 400mg-18mg or 400mg-9mg for 3 days.

- For participants <45 kg of body weight at baseline: FDC of 400mg ALB-9mg IVM.
- For participants ≥45 kg of body weight at baseline: FDC of 400mg ALB-18mg IVM.

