SubGroup 1 (n=4): +3h, +6h SubGroup 2 (n=4): +4h, +24h SubGroup 3 (n=4): +2h, +8h SubGroup 4 (n=4): +5h, +7h SubGroup 5 (n=4): +1h, +7h SubGroup 6 (n=3): +2h, +24h SubGroup 7 (n=3): +4h, +8h

For Arm 2 (albendazole + ivermectin treatment), the 11 points (+1h, +2h, +3h, +4h, +5h, +6h, +7h, +8h, +24h, +48h, +72h) has been divided in 2 groups:

i) One group of 6 points comprising the points from +1h until +6h

ii) One group of 5 points comprising the points from +7h until +72h

For assigning the 2 points we randomize 1 time from each group For Arm 2 (10 groups of 5 participants):

SubGroup 1 (n=5): +4h, +72h SubGroup 2 (n=5): +5h, +48h SubGroup 3 (n=5): +2h, +8h SubGroup 4 (n=5): +1h, +8h SubGroup 5 (n=5): +3h, +72h SubGroup 6 (n=5): +4h, +24h SubGroup 7 (n=5): +3h, +7h SubGroup 8 (n=5): +2h, +48h SubGroup 9 (n=5): +5h, +7h

For Arm 3 (10 groups of 5 participants), (albendazole + ivermectin treatment x 3 consecutive days), we follow the same schedules as for Arm 2, but adding predose on Day 2 and starting the extractions from that point, as follows

SubGroup 1 (n=5): predose Day 2, +4h, +72h SubGroup 2 (n=5): predose Day 2, +5h, +48h SubGroup 3 (n=5): predose Day 2, +2h, +8h SubGroup 4 (n=5): predose Day 2, +1h, +8h SubGroup 5 (n=5): predose Day 2, +3h, +72h SubGroup 6 (n=5): predose Day 2, +4h, +24h SubGroup 7 (n=5): predose Day 2, +3h, +7h SubGroup 8 (n=5): predose Day 2, +2h, +48h SubGroup 9 (n=5): predose Day 2, +5h, +7h SubGroup 10 (n=5): predose Day 2, +1h, +24h

Global Health

Sensitivity analysis populations

ISGIODAI Barcelona Institute for

Safety sensitive populations: A per-protocol analysis will be performed including all randomized participants who received at least one dose of medication.

Efficacy sensitive population: A per-protocol analysis will be conducted, including all randomized participants who received at least one dose of medication, did not withdraw, without major protocol deviations, and were not lost to follow-up. Also, participants who did not meet the inclusion or exclusion criteria, received an incorrect treatment, or were administered an incorrect dose will be excluded from the per-protocol analysis.

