5.4.1 Secondary efficacy outcomes analysis

The analysis will be conducted on the ITT population and in the sensitivity population (per protocol)

The secondary efficacy endpoints for the phase II and phase III are the following:

- CR for *T. trichiura* 21 days after treatment, as determined by microscopy (phase II).
- CR for hookworm and *S. stercoralis* 21 days after treatment, as determined by microscopy (phase II and phase III).
- ERR for *T. trichiura* 21 days after treatment, by microscopy (phase II and phase III).
- ERR for hookworm 21 days after treatment, by microscopy (phase II and phase III).
- CR for *T. trichiura*, hookworm and *S. stercoralis*, by PCR (phase II and phase III).
- Parasite burden decrease after 21 days for *T. trichiura*, hookworm, and *S. stercoralis*, by PCR (phase and phase III).

The first 2 endpoints above regarding the CR will be analyzed using the same approach as the primary endpoint analysis.

Egg reduction rate (ERR) for each species (for *T. trichiura* and hookworms) at end of treatment period will be estimated. *S. stercoralis* will not be evaluated by this analysis.

$$ERR (geometric mean) = 1 - \frac{e^{\frac{1}{n}\sum\log(EPG \ follow \ up+1)} - 1}{e^{\frac{1}{n}\sum\log(EPG \ baseline+1)} - 1}$$

The logarithmic transformation will be conducted. As there may be participants with a count of zero eggs in the post-treatment stool sample, a value of 1 will be added to total egg count at baseline and total egg count at post-treatment so that the logarithmic transformation can be applied. The geometric mean will be used to summarize the mean egg count at pre-treatment and post-treatment visits and in the calculation of the mean percent egg reduction. Treatment differences will be evaluated by an analysis of covariance (ANCOVA), in which the logarithm of the egg count at post-treatment is the dependent variable, site (if appropriate), and treatment as fixed effect, and the logarithm of the egg count at pre-treatment is the covariate. Baseline egg count will also be analysed as an independent variable that conditions treatment response [11].

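### SAP 3.3 misstates the Phase II Group 2 tablet; if 18 mg was given as the protocol says, about 6% of each pooled FDC arm had twice the Phase III dose for their weight (minor)

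*SAP*

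**What the plan says.** **Pooling.** SAP 5.4 (Primary efficacy outcomes analysis) says "The analysis will include both Phase II and Phase III participants", for both the ITT and the per-protocol set. The CMH test is stratified at most by site, "controlling the effect of site if that is appropriate (sufficient participants"). Protocol 2.2 (Rationale for the adaptive design) also foresees a final analysis on the data of both phases.

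**Phase II Group 2.** Protocol 6.1.2: "Group 2 will receive FDC in an Albendazole 400mg/Ivermectin 18mg comp". SAP 3.1 agrees: "Group 2 (38 participants): with body weight of [30-45] Kg will receive 400-600" µg/kg, with the 400mg-18mg tablet.

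**Phase III.** Protocol 6.1.2: "For participants <45 kg of body weight at baseline: FDC of 400mg ALB-9mg IVM". The 18 mg tablet starts at 45 kg.

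**The conflicting text.** SAP 3.3 describes Phase II Group 2 as receiving 400-600 µg/kg and then adds "Participants <45 kg: FDC of 400mg ALB-9mg IVM", with 18 mg only from 45 kg.

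**Related analyses.**
- SAP 4.1: participants who "were administered an incorrect dose will be excluded from the per-protocol analysis".
- SAP 5.4.1: a secondary *T. trichiura* cure rate "21 days after treatment, as determined by microscopy (phase II"), so for Phase II alone.
- SAP 5.4.3: a subgroup split at 400 µg/kg of ivermectin.

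**Randomisation.** SAP 3.4 uses simple randomisation within weight groups in Phase II (0.2/0.4/0.4) and blocks stratified by species in Phase III. For the Phase III ratio, protocol 4.1 (Method of Allocation) says 1:1:1, and SAP 3.3 says 0.2/0.4/0.4.

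**The concern.** There are two linked problems.

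First, the SAP disagrees with itself and with the protocol on the tablet that one Phase II weight group received. A SAP should not be ambiguous on dose when one of its analysis sets excludes participants for an incorrect dose.

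Second, if the protocol was followed, children of 30 to just under 45 kg in the same named arm received 18 mg in Phase II and 9 mg in Phase III. The pooled FDC and FDCx3 cure rates then do not strictly describe the weight-banded regimen tested in Phase III. No planned analysis is limited to that regimen with its concurrent ALB control. What is at stake is which regimen the estimated cure rate describes, not whether the test against ALB is valid.

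**Working it through.** **Step 1. The plan's own power.** Inputs from protocol 9.2, Table 1: evaluable 116/223/223 (ALB/FDC/FDCx3), cure 23.7%/43.7%/59%, two-sided alpha 0.05/3 = 0.0167. The method is the two-proportion z test with pooled variance under the null and no continuity correction.

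| Comparison | Recomputed | Stated |
|---|---|---|
| ALB vs FDC | 90.6% | 91% |
| ALB vs FDCx3 | >99.9% | 100% |
| FDC vs FDCx3 | 80.2% | 80% |

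The plan's figures are reproduced.

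**Step 2. Dose by tablet** (µg/kg = 1000 × mg / kg).

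| Weight | 9 mg | 18 mg |
|---|---|---|
| 30 kg | 300 | 600 |
| 44 kg | 205 | 409 |
| 44.9 kg | 200 | 401 |

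The two ranges do not overlap. The 9 mg in SAP 3.3 cannot reach 400 µg/kg anywhere in this band, so that bullet contradicts itself. A child of exactly 45 kg gets 18 mg under both rules.

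**Step 3. Share of the pooled arms.** Group 2 has 38 children. At 0.2/0.4/0.4 that is 38 × 0.4 = 15.2 per FDC arm and 38 × 0.2 = 7.6 on ALB. The shares are 15.2/248 = 6.1% and 7.6/129 = 5.9%. Groups 1 and 3 (38 + 50 = 88 of 126) received 9 mg and already follow the Phase III rule.

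**Step 4. Shift in a pooled FDC cure rate.** Shift = 0.061 × dose effect. The documents give no figure for the effect of doubling the dose within this weight band, so a range is assumed.

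| Assumed gain in cure from doubling | Shift in pooled rate |
|---|---|
| 5 points | 0.3 |
| 10 points | 0.6 |
| 20 points | 1.2 |
| 30 points | 1.8 |

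The planned differences from ALB are 43.7 − 23.7 = 20.0 and 59 − 23.7 = 35.3 points. Between FDC and FDCx3 the shift largely cancels if it is similar in both arms.

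**Step 5. What the planned exposure subgroup shows.** 18 mg exceeds 400 µg/kg below 18000/400 = 45 kg, and 9 mg exceeds it below 9000/400 = 22.5 kg. In the FDC arms, the ≤400 stratum therefore contains no Group 2 child below 45 kg on 18 mg. It also loses the children below 22.5 kg who do follow the Phase III rule, and ivermectin exposure is undefined on ALB. The Phase II-only cure rate mixes Group 2 with the 88 conforming children. Taking it away from the pooled result would leave Phase III alone.

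**Step 6. Power of a restricted analysis** (same formula).

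| Set | Evaluable | ALB vs FDC | ALB vs FDCx3 | FDC vs FDCx3 |
|---|---|---|---|---|
| Without Group 2 | 109/209/209 | 88.4% | >99.9% | 77.2% |
| Phase III only | 93/178/178 | 81.8% | >99.9% | 69.1% |

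The evaluable numbers without Group 2 are 116 − 7.6 × 0.9 and 223 − 15.2 × 0.9. Phase III numbers are from Table 2.

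**Step 7. Does a phase stratum remove the dose mixing?** Take a 10-point dose effect and Table 2 numbers, with ALB vs FDC of 26 vs 50 in Phase II and 103 vs 198 in Phase III. Phase II difference = 20 + 10 × 15.2/50 = 23.04; Phase III difference = 20. Mantel-Haenszel weights are 26 × 50/76 = 17.1 and 103 × 198/301 = 67.8. The weighted difference is (17.1 × 23.04 + 67.8 × 20)/84.9 = 20.61. Without the stratum it is 20 + 0.61 = 20.61. The stratum does not touch the mixing. Its purpose is to protect against different arm ratios in the two phases.

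**The case against.** **A reader might infer that SAP 3.3 will remove correctly dosed Group 2 children from the FDC arms of the per-protocol set and leave their ALB counterparts in.** Read in isolation it could: about 15 of 50 Phase II children per FDC arm and none of 26 on ALB. The documents do not support expecting this. Protocol 10.1.9 defines a deviation as noncompliance with the protocol, SAP 5.2.2 has deviations identified and categorised in the eCRF, and the protocol gives 18 mg throughout, including its kilogram-by-kilogram table. The SAP 3.3 parenthesis repeats the Phase III weight rule and looks like a drafting slip. It would also affect only a sensitivity analysis. This objection stands, and the per-protocol risk remains a remote literal reading.

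**A reader might also infer that pooling biases the comparison with ALB.** It does not. Group 2 was randomised to all three arms, pooling is prespecified, and the 625 in the sample size include the 126 from Phase II. Even a 45-point effect would shift the pooled rate by only about 2.8 points. That figure takes the 88.6% cited in protocol 2.2 for 600 µg/kg minus the planned 43.7%, a cross-study comparison. No conclusion is shown to be at risk.

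**The exposure is not new to the arm.** Phase III children below 22.5 kg on 9 mg already receive 400-600 µg/kg. This stands: Group 2 changes which weights get which dose, not the overall range.

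**Planned analyses already cover part of this.** The ≤400 stratum does leave out the off-rule children in the FDC arms. This stands in part, for the reasons in step 5 of the working.

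**The phase stratum removes no demonstrated bias.** At Table 2 numbers both phases have the same ratio (26/50/50 and 103/198/198), so this stands for the planned allocation. It does not settle the matter, because protocol 4.1 gives 1:1:1 for Phase III. If that ratio was used, arm shares would differ by phase within Kenya, and site strata alone would not separate them.

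**Conclusion.** This is a minor point, and it holds in three parts.

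1. SAP 3.3 is wrong as written on the Group 2 tablet. This follows from the text and the dose arithmetic, without assumptions.
2. If 18 mg was given, about 6% of each pooled FDC arm had twice the Phase III dose for their weight. The comparison with ALB stays valid. The pooled cure rate shifts by about 0.3-1.8 points, which rests on the assumed 5-30 point dose effect and on all 38 Group 2 children being below 45 kg (so it is an upper count). If records show that 9 mg was given, this part falls away.
3. The planned ≤400 µg/kg subgroup shows the Phase III regimen only in part, so one supportive table is worth having.

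The phase stratum is justified by the separate randomisation and the conflicting Phase III ratios, not by the dose mixing.

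**What to change.** 1. **Correct SAP 3.3** so that Group 2 receives 18 mg (400-600 µg/kg), as in protocol 6.1.2 and SAP 3.1, or whatever was actually given. State that 18 mg in Group 2 is not an incorrect dose for the per-protocol set. Cost: one or two sentences.
2. **Keep the pooled ITT primary analysis.** If 18 mg was given, add one supportive analysis that omits Phase II Group 2 participants below 45 kg from all three arms, ALB included, so that it stays a randomised comparison. Cost: one table. Power is about 88%, >99% and 77%, some 2-3 points below the pooled set for ALB vs FDC and FDC vs FDCx3. This keeps the 88 conforming Phase II children, which a Phase III-only analysis would lose.
3. **Add phase to the CMH site strata**: Kenya Phase II, Kenya Phase III, Ethiopia, Mozambique. It drops no one and costs essentially no power. In a simulation of FDC vs FDCx3 with an assumed 60/20/20 split of Phase III over sites, power was 79.5% with site strata and 79.9% with site by phase. It guards against phase-by-arm imbalance and does not replace step 2.

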#### **Rationale for Study Population Selection**

Participants between 5 and 18 years of age will be screened. This age range has been selected because of the high prevalence of STH in this population (it is the group most affected with STH), and the beneficial logistics implications of recruiting/enrolling at schools. The total number of participants to be screened depends on the prevalence rates of STH at the study site(s). A participant infected with a mixture of worms will be counted in the sample size for each worm that the participant is infected.

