# 9.5.2 ANALYSIS OF THE PRIMARY ENDPOINT(S)

The primary safety endpoints in phase II, are the frequency, type, severity and relationship to study drug for all adverse events and severe adverse events.

The primary efficacy endpoints for the efficacy phase III trial the cure rates for *T. trichiura* and 21 days after treatment using microscopy. Cochran–Mantel–Haenszel (CMH) test, controlling the effect of site if that is appropriate (sufficient participants), will be used to compare the cure rates for the 3 treatment

Version 4.0

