3.4 Randomisation

In the phase II component, participants with *T. trichiura* infection (confirmed by Kato-Katz technique in a fresh stool sample) will be enrolled in a sequential manner per weight group in order to administer the desired dose, starting from 300-391 μ g/kg ivermectin. Participants in the phase II trial will be stratified in different weight groups: Group 1 (23-<30 kg) 38 participants, group 2 (30-45 kg) 38 participants and group 3 (15-23 kg) 50 participants in order to gradually increase the dose of ivermectin in the FDC. Then, participants will be allocated by simple randomization to one of the three study arms with unequal probability (ALB: p=0.2, n=26; FDCx1: p=0.4, n=50; FDCx3: p=0.4, n=50) In the phase III component, allocation of participants to study arms will be done by block randomization and stratified by STH species. We will ensure balanced allocation to the three arms in the three study countries. Treatment allocation for each study participant will be concealed in opaque sealed envelopes that will be opened only after enrolment. Study participants will be assigned a unique study number linked to the allocated treatment group. Participants will be randomly allocated with unequal probability, according to the specific expected cure rate of each species.

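### The primary CMH test omits the species list that Phase III is randomised by and leaves site optional, while the allocation passages conflict; any bias is small and conditional, but some stated powers fail under some readings

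*SAP*

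**What the plan says.** **Randomisation.** In Phase III, "allocation of participants to study arms will be done by block randomization and stratified by STH species" (SAP 3.4; protocol 4.1 agrees). Protocol 6.3 adds that each of the three institutions is randomised separately.

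**Primary test.** The CMH test of SAP 5.4 is specified as follows: "controlling the effect of site if that is appropriate (sufficient participants), will be used to compare the cure rates for the 3 treatment groups". Protocol 9.5.2 has the same condition, "controlling the effect of site if that is appropriate (sufficient participants"). Neither says how many participants are enough, and neither names the species list. SAP 5.4.1 uses the same method for the microscopy cure rates of the other species.

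**Who enters each analysis.** SAP 5.4: "The analysis will include both Phase II and Phase III participants", and "A participant with multiple infections will be included in the analysis of each target species that the participant is infected with". Protocol 4.2: "A participant infected with a mixture of worms will be counted in the sample size for each worm that the participant is infected". Protocol 6.3 says co-infected children are allocated in the same way as those with one infection, but not from which species list.

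**Allocation ratio.**
- SAP 3.3, Phase III: one ratio, 0.2/0.4/0.4.
- SAP 3.4, Phase III: "Participants will be randomly allocated with unequal probability, according to the specific expected cure rate of each species", with no numbers, and also "We will ensure balanced allocation to the three arms in the three study countries".
- Protocol Table 2 and SAP Table 4: counts whose ratio differs by species.
- Protocol 4.1, Phase III: 1:1:1.
- Phase II: 0.2/0.4/0.4 in the protocol synopsis and SAP 3.4, but equal probability in protocol 6.1.2.
- Protocol 9.2 and SAP 3.5, text: Phase III arm totals of 251 ALB, 427 FDC and 419 FDCx3.

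**The concern.** An analysis should respect the groups within which participants were randomised, above all when the allocation ratio differs between them. A co-infected child can enter the *T. trichiura* analysis after being randomised on the hookworm or *S. stercoralis* list. If those lists have different albendazole shares, the arms of the primary analysis hold different mixes of lists. If cure also differs between lists, the crude comparison with albendazole is shifted, and stratifying by site does not remove the shift.

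Two further things are at stake. The site clause leaves the strata of the primary test to be settled after the data are seen. And the stated power depends on a ratio that the documents do not agree on.

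**Working it through.** **1. Reproduce the plan's power.** Inputs: cure rates and evaluable numbers from protocol Table 1 / SAP Table 3; two-sided alpha 0.05/3 = 0.0167. Formula, with p̄ the pooled rate:

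power = Φ[(|p1 − p2| − z·√(p̄(1 − p̄)(1/n1 + 1/n2))) / √(p1(1 − p1)/n1 + p2(1 − p2)/n2)]

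| Comparison | n | Cure rates | Stated | Computed |
|---|---|---|---|---|
| *T. trichiura* ALB vs FDC | 116, 223 | 23.7%, 43.7% | 91% | 90.6% |
| *T. trichiura* FDC vs FDCx3 | 223, 223 | 43.7%, 59% | 80% | 80.2% |
| *S. stercoralis* FDC vs FDCx3 | 108, 107 | 79%, 94% | 80% | 80.0% |
| Hookworm ALB vs FDCx3 | 91, 99 | 79.5%, 95% | 82% | 80.1% |

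The figures reproduce, to within 2 points for hookworm.

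**2. Albendazole share by list** (protocol Table 2 / SAP Table 4).
- *T. trichiura*: Phase II 26/126 = 20.6%; Phase III 103/499 = 20.6%
- *S. stercoralis*: 47/286 = 16.4%
- Hookworm: 101/312 = 32.4%

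The two phases have the same share, so pooling them causes no shift under the table. The Phase III columns sum to ALB 103 + 47 + 101 = 251, FDC 198 + 120 + 101 = 419 and FDCx3 198 + 119 + 110 = 427. The text has the last two swapped.

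**3. Shift in the primary comparison.** The documents give neither the overlap nor a cure gap, so both are assumed. Let a share f of the hookworm list carry *T. trichiura*, with cure differing by d points. The hookworm-list share of the *T. trichiura* analysis is 101f/(129 + 101f) in ALB and 101f/(248 + 101f) in FDC. The shift in ALB vs FDC is the difference in shares times d.

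| f | ALB share | FDC share | Shift, d = 10 | Shift, d = 20 |
|---|---|---|---|---|
| 10% | 0.073 | 0.039 | 0.3 | 0.7 |
| 30% | 0.190 | 0.109 | 0.8 | 1.6 |
| 100% | 0.439 | 0.289 | 1.5 | 3.0 |

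The sign follows the gap: higher cure on the hookworm list flatters ALB, lower cure flatters FDC. If the *S. stercoralis* list contributes at the same rate and gap, it partly offsets this: 0.4, 0.9 and 1.3 points at d = 20.

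**4. Type I error.** Three-group CMH, nominal 5%, 200,000 simulated trials per setting, cure 23.7% in every arm of the *T. trichiura* list, gap in either direction.

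| f | Unstratified, d = 10 | Unstratified, d = 20 |
|---|---|---|
| 10% | 5.0% | 4.9–5.1% |
| 30% | 5.0–5.3% | 5.6–5.8% |
| 100% | 6.2–6.3% | 9.8–11.3% (9.0% in a variant where sites differ by ±5 points) |

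Stratified by list, the error is 4.9–5.1%. Stratified by site only, at d = 20 with the hookworm list spread equally over sites, it is 5.0%, 5.7% and 8.7%. The pairwise ALB vs FDC test is a little more exposed: 6.4–6.7% at nominal 5% with f = 30% and d = 20.

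**5. Omitting site.** For FDC vs FDCx3 with three equal sites, power is 79.6% without site and 81.4% with it if site cure rates differ by ±10 points, and 80.1% vs 82.8% at ±15. The loss is 1.8 to 2.7 points.

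**6. Power under the other stated ratios** (formula of step 1, same evaluable total per species).
- 0.2/0.4/0.4 on every list. Hookworm, 281 split 56/112/112: ALB vs FDCx3 74% (stated 82%), FDC vs FDCx3 87% (stated 80%). *S. stercoralis* FDC vs FDCx3: 78% (stated 80%).
- 1:1:1 in Phase III, Phase II as tabled. *T. trichiura* 173/195/195: ALB vs FDC 95% (stated 91%), FDC vs FDCx3 74% (stated 80%).

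**The case against.** The bias needs three things together, and none is documented: list-specific ratios in use, *T. trichiura* carriers randomised on another list, and different cure between lists. The only Phase III probabilities that the SAP gives as numbers are 0.2/0.4/0.4, and with one ratio on all lists there is no bias. Nor does any passage send a *T. trichiura* carrier to the hookworm list; if every carrier uses the *T. trichiura* list, the primary analysis is unaffected. This stands, and it is why the point is conditional.

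The SAP also plans a mono-infected vs co-infected subgroup analysis of the primary outcome (5.4.3). Mono-infected *T. trichiura* children all share one list, so that subgroup could expose a distortion. It does not replace correct strata in the primary test.

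A reader might infer that the primary test has roughly double its nominal error rate. The 9–11% figures arise only if every hookworm-list child carries *T. trichiura* and cure differs by 20 points. Protocol 10.2 makes that implausible: it describes the Ethiopian site as high in hookworm and *S. stercoralis*, and reports hookworm with *T. trichiura* in the Kenyan area.

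A reader might also infer that pooling the phases or dropping site biases the result. Under the table, pooling phases shifts nothing. Dropping site costs only precision if allocation is balanced across countries as stated, and the loss computed above is for FDC vs FDCx3, which is not in the stated primary hypothesis.

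Finally, the ratio conflict does not only lower power: each alternative raises it for one comparison and lowers it for another.

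**Conclusion.** The point holds as a fault of specification. The primary test does not follow the randomisation, its strata are not fixed in advance, and the allocation passages cannot all be true.

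If all three conditions hold, with overlap of 10–30% and cure gaps of 10–20 points (both assumed), the shift in ALB vs FDC is about 0.3 to 1.6 points and the three-group type I error about 5–6%. Against a planned difference of 43.7 − 23.7 = 20.0 points, this will not change the main conclusion. If any one condition fails, the bias in the primary analysis is zero.

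The ratio conflict matters more for planning. Two comparisons designed for 80% power fall to 74%: hookworm ALB vs FDCx3 under 0.2/0.4/0.4 on every list, and *T. trichiura* FDC vs FDCx3 under 1:1:1 in Phase III. The documents do not show which ratio was used, so neither loss can be taken as fact. The change is worth making because it costs little and some correction is needed under every reading.

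**What to change.** 1. Reconcile the allocation statements in the protocol synopsis, 4.1, 6.1.2 and 9.2 and in SAP 3.3 to 3.5 with Tables 2 and 4, including the swapped 427 and 419. State the ratio for each list and which list a co-infected child is randomised from. Keep that list as an analysis variable. Restate the power for the confirmed ratio.

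2. In SAP 5.4 and protocol 9.5.2, replace the site clause with: *The CMH test will be stratified by site and by the species list used for randomisation; within a list, sites with sparse cells are combined, and lists with different allocation ratios are not combined.* No minimum count per arm is needed, because the CMH test tolerates sparse strata. Phase need be a stratum only if the confirmed Phase II and Phase III ratios differ.

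3. Use the same strata for the hookworm and *S. stercoralis* cure rates in SAP 5.4.1.

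Cost: wording in both documents, slight programming work, one retained variable, and a little information lost in very small strata. For example, at 10% overlap the *S. stercoralis* list would add only about 47 × 0.1 = 4.7 ALB children to the *T. trichiura* analysis.
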